6.8. POOLING OF CENTERS

Analysis will be pooled overall and by cohort (A vs. B).

6.9. SUBGROUPS

The following subgroups will be utilized for some efficacy analyses and adverse event summarizations:

Version 2.0

Syneos Health #1009529A

Age: 2- <6 years, 6-<12 years, 12 - <18, 2-<18 years, \geq 18 - 35 years.

Sex: Male, Female

Baseline Weight: <37.5 kg vs. ≥ 37.5 kg

Number of concomitant Antiepileptic Medications Used: ≤ 2 , 3, ≥ 4 medications

Number of prior Antiepileptic Medications Used: 0-3, 4-6, 7-9, ≥10 medications

Baseline Frequency of Seizures that Result in Drops (events/28 days): based on observed tertiles

Usage of a specific concomitant medication(s) (top 3 concomitant AEDs to be determined by data review) (Yes / No)

7. DEMOGRAPHIC, OTHER BASELINE CHARACTERISTICS AND MEDICATION

7.1. SUBJECT DISPOSITION AND WITHDRAWALS

The Part 1 subject disposition will be presented per treatment group and overall for Cohort A and B independently.

For describing the Part 1 subject disposition, the following will be summarized by number and percentage:

- Subjects enrolled (only overall)
- Subjects enrolled but not randomized and reason for not-randomized (only overall)
- Subjects randomized
- Subjects in SAF
- Subjects in mITTs
- Subjects in PP
- Subjects assigned to SAF, mITT, PP and discontinued the study and reason.
- Number of subjects in the trial per trial period/phase (Titration Phase, Maintenance Phase, Taper Period for those not entering Part 2, and Follow-up Period) will be presented for SAF and mITT sets.
- Trial completers
 - Trial completers continuing into Part 2

Trial completers not continuing into Part 2 and reason for not continuing Part 1 trial completers include: 1.) subjects who did not discontinue prior to the Visit 12, and 2.) subjects who completed at least through Visit 8 and enrolled into the Part 2 open label extension.

For subjects enrolled but not randomized to treatment in Part 1, and for the tallies listed under each reason for not being randomized, the denominator used to calculate the percentage will be the number of enrolled subjects. For all other calculations in the Part 1 disposition table, the denominator will be the number of subjects randomized.

All subject disposition data will be listed using the enrolled population and sorted by treatment and site.

7.2. DEMOGRAPHIC AND OTHER BASELINE CHARACTERISTICS

Part 1 subject demographics and baseline characteristics will be summarized descriptively per treatment group and overall, for the SAF and mITT populations for Cohort A and B.

The following demographic characteristics will be summarized:

- Age [Years]
- Categorized age as: 2 <6 years, \geq 6 <12 years; \geq 12 <18 years, \geq 18 35 years
- Sex
- Race
- Ethnicity
- Height [m]
- Weight [kg]
- BMI [kg/m²]
- Geography: North America, Europe, Australia, Japan (Cohort B analysis only)

All subject demographics data will be listed for the enrolled population.

- If the start day and month are missing but the start year is complete, a medication will only be excluded as concomitant if the start year is before the year of study drug administration and if the stop date (either full date, month and year if missing day, or year if missing month and day) is before study drug administration.
- If the start date is completely missing and the stop date is prior to first dose or completely missing, the medication will be assumed to be a prior medication.

A medication may be counted as concomitant in Part 1 and in Part 2. By definition, a prior medication cannot be counted as concomitant in Part 1. Medication will be summarized and sorted alphabetically separately for prior and concomitant medication by Anatomical Therapeutic Chemical (ATC) categories (Level 2: pharmacological or therapeutic subgroup and Level 3: chemical or therapeutic or pharmacological subgroup) and WHO-DD drug code. For each medication the number and percentage of subjects will be displayed.

Part 1 medication summary tables will be presented for the SAF population.

All prior and concomitant medications/treatments will be listed for the enrolled population.

7.4.1. Prior and Concomitant Antiepileptic Treatments

Medication (collected on the prior antiepileptic medications, prior medications, and concomitant medications eCRF page) will be coded using the World Health Organization Drug Dictionary (WHO-DD) Format B3 Version Sep2017 or later. Anti-epileptic medications will be identified using any drug entered on the prior-antiepileptic medication page and anti-seizure concomitant medications with indication of "Lennox-Gestaut Syndrome".

Prior and concomitant antiepileptic medications will be defined and analyzed for the SAF and OLE similar to concomitant medications as described in Section 7.4.

All prior and concomitant antiepileptic treatments will be listed for the enrolled population.

Note that further summaries of rescue medications recorded on the daily medication diary are described in the efficacy section.

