Listings of the most extreme values for a subject recorded in Part 1 and Part 2 will be created for each parameter. These will show the lowest recorded value and the highest recorded value noted for the subject. A listing of subjects with markedly abnormal laboratory results will be provided, and additional explorations of the data may be conducted as warranted.

Additionally, summaries of abnormal lab results by parameter will be provided to investigate changes in platelet count and prolactin in detail. The summaries include:

- Subjects with decrease (≥25% from baseline) in Platelets count with normal platelet count at baseline
- Subjects with decrease (≥25% from baseline) in Platelets count relative to baseline (whether normal or abnormal) platelet count
- Subjects with decrease (≥25% from baseline) in Platelets count with normal platelet count at baseline, by valproate use
- Subjects with decrease (≥25% from baseline) in Platelets count with normal platelet count at baseline, by presence/absence of infection event prior to 7 days of the lab assessment
- Subjects with increase (≥25% from baseline) in prolactin with normal baseline
- Subjects with increase (≥25% from baseline) in prolactin with normal baseline, and had seizure event within 48 hours prior to prolactin

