Medications were collected on the "Prior Antiepiletic Drugs", "Concomitant Medications", or "Rescue Medications" eCRF pages. Medication start and stop dates were only collected on the Concomitant Medications eCRF pages. Prior medications (ie, non-antiepileptic and non-concomitant drugs) were derived from the Concomitant Medications eCRF page and therefore only included medications that were stopped during the period from 30 days prior to the screening date to the day before first date of study treatment. This was incorporated into Cohort A outputs Table 14.1.4.1.1 and Listing 16.2.4.3.1.1. This will also be incorporated into Table 14.1.4.1.2 and Listing 16.2.4.3.1.2 for Cohort B.

New Efficacy Analyses

New Seizure Types

A post-hoc analysis of the emergence of new seizure types will be performed. The summary of this variable will be based on the Seizure History eCRF (a form that lists both previous and current seizure types experienced by each subject), seizures reported on the seizure diary prior the start of study treatment, and seizures reported during the Titration and Maintenance (T+M) Period of Part 1. Each

This document is confidential.

Controlled Document ID: 1600A.01, Effective Date 29-Nov-2018 Version Date: 31JUN2021 Filing requirement: TMF/PMF

subject's unique seizure types experienced prior to study treatment will be determined from the following types:

Seizures Types

Generalized Tonic-Clonic (GTC)

Secondarily Generalized Tonic-Clonic (SGTC)

Tonic

Atonic

Tonic/Atonic

Clonic

Hemiclonic L Body

Hemiclonic R Body

Hemiclonic with Independent L and R

Focal with clear observable signs

Focal without clear observable signs

Myoclonic

Absence/atypical absence

Infantile Spasms

Epileptic Spasms

ure type during '
is defined '
CRE 2 Other
Subjects with emergence of at least one new seizure type during the T+M Period will be summarized by randomized treatment group. A new seizure type is defined as a seizure type recorded in the seizure diary that was not recorded in the Seizure History eCRF as occurring before the first study drug dose date and that also did not occur during the Baseline Period.

All Countable Seizures that did not Result in Drops (ESC Confirmed)

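### Section 7.4.1 makes concomitant-AED status depend on the recorded indication, so an anti-seizure drug entered for 'seizures' or 'epilepsy' may not be counted

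*SAP*

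**What the plan says.** Section 7.4.1 fixes the rule by two routes. A drug counts as an AED if it is on the prior-AED page, whatever its indication, or if it is among the "anti-seizure concomitant medications with indication of" one named syndrome, printed there as 'Lennox-Gestaut'. The source records are those "collected on the prior antiepileptic medications, prior medications, and concomitant medications eCRF page". The section adds that prior and concomitant AEDs are defined in the same way as other medications under section 7.4.

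Section 7.4 gives the date rules. One of them covers undated records: "If the start date is completely missing and the stop date is prior to first dose or completely missing, the medication will be assumed". The status assumed there is prior. The section also states: "By definition, a prior medication cannot be counted as concomitant in Part 1".

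Section 3 of the SAP addendum names three medication pages (prior AEDs, concomitant medications, rescue medications) and reports: "Medication start and stop dates were only collected on the Concomitant Medications eCRF pages". The addendum does not change the 7.4.1 rule.

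Sections 7.4 and 7.4.1 have the drugs coded in WHO-DD, and section 7.4 summarises them by ATC levels 2 and 3. Section 7.4.1 does not use that coding to decide what an AED is.

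**The concern.** The second route sets two conditions. The drug must be anti-seizure, and its indication must be the syndrome. A drug already recognised as anti-seizure is dropped if the site entered seizures, epilepsy or a seizure type as the reason for use. Whether a drug counts then depends on site wording and not on the treatment the subject takes.

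The uses of the concomitant-AED flag are:

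- the efficacy subgroup by number of concomitant AEDs (≤2, 3, ≥4) in section 6.9, tabulated for drop seizures and for investigator CGI-I;
- the AED sensitivity analysis in 8.2.3, which classifies subjects by number of concomitant AEDs in T+M and compares arms on AED changes with Fisher's exact test;
- the concomitant antiepileptic treatment tables;
- TEAEs and related TEAEs by commonly used concomitant AED (section 9.3.2).

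The 8.2.3 analysis is the most sensitive of these. It exists to detect departures from stable background therapy. A drug added on study might be recorded under the event that prompted it and not under the syndrome. That is an inference about how sites record data, not something the documents show.

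**Working it through.** The plan gives no figure to reproduce, so the rule was traced first and then its possible size worked out.

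**Tracing the rule.** Take an anti-seizure drug that the subject takes throughout Part 1, entered on the Concomitant Medications page with the indication 'epilepsy'.

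1. Route 2 (concomitant page plus syndrome indication): the indication is not Lennox-Gastaut syndrome, so the record fails.
2. Route 1 (prior-AED page): suppose the same drug is also entered there. By the addendum that page holds no dates. By section 7.4 a record with neither start nor stop date is prior, and a prior medication is not concomitant in Part 1.
3. Neither route makes the drug a concomitant AED.

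The result changes only if a drug named on the prior-AED page is taken as an AED wherever it appears, so that its dated concomitant record is classified by the 7.4 date rules. Section 7.4.1 could be applied that way but does not say so.

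The printed spelling 'Gestaut' adds a smaller problem: an exact text match on it would also miss correctly spelled entries.

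**Possible size.** Let q be the share of concomitant AED records carrying another indication term. The documents do not give q; the range 0.10 to 0.50 is assumed. A subject on three AEDs moves from the '3' stratum to '≤2' if at least one record is missed.

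- Wording identical for all of a subject's AEDs: P = q, which gives 0.10 to 0.50.
- Records independent within a subject: P = 1 − (1 − q)³. For q = 0.10, 1 − 0.9³ = 1 − 0.729 = 0.271. For q = 0.50, 1 − 0.5³ = 1 − 0.125 = 0.875.

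Site wording is likely to be similar across one subject's records, so the first line is probably nearer than the second. If the eCRF forced the syndrome term, q is 0 and nothing is lost.

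**The case against.** The strongest case against runs as follows.

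- **The rule has two routes.** It would be wrong to say that AEDs in general are recognised only through the syndrome indication, because any drug on the prior-AED page qualifies whatever its indication. This stands. The point is limited to concomitant status. Nor do the documents say that the prior-AED page is limited to stopped drugs, so the look-up reading remains open. What does not stand is that the SAP specifies that reading.
- **No misclassification is shown.** Every subject has the syndrome, and the documents do not say whether indication was free text or a fixed term. This stands. The defect is in the rule as fixed.
- **Several uses drop out.** The platelet summary in 9.10 ("Platelets count with normal platelet count at baseline, by valproate use") names a drug and does not refer to the 7.4.1 flag. The top-three-AED subgroup in 6.9 has no drop-seizure efficacy table in either index. The tables of TEAEs by number of AEDs are in the SAP index but not in the addendum's current one. All of this stands, and these uses are not counted here.
- **AED changes are caught elsewhere.** Changes in AED dose or type are protocol violations under 8.2.3 and lead to per-protocol exclusion. Deviations are reviewed before lock and unblinding (sections 6.4 and 6.5), and all concomitant drugs are tabulated by ATC class. This stands, so such changes would not go unseen. The 8.2.3 comparison could still miss them.
- **Randomised, blinded treatment gives no evident reason for background-AED wording to differ by arm.** This stands for background drugs.
- **The indication test keeps out AED-class drugs taken for other reasons.** This is true, but it does not require limiting the accepted indication to one syndrome name.

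**Conclusion.** The point holds. As written, concomitant-AED status depends on indication text, and an anti-seizure drug recorded for seizures or epilepsy would not be counted. The affected outputs are the subgroup by number of concomitant AEDs, the AED-change analysis and Fisher comparison in 8.2.3, the concomitant-AED tables, and TEAEs by commonly used AED. This rests on the date rules in 7.4, on the addendum's statement about dates, and on the prior-AED page not being used as a drug-name look-up.

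The size is unknown. Under the assumed 10% to 50% of records, a three-AED subject is undercounted with probability between 10% and 88%, depending on how far wording clusters within the subject.

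A reader might infer that the efficacy conclusion is at risk. The documents do not support that: neither the primary rank ANCOVA nor the key secondary tests use the AED flag. A reader might also infer that AEDs were in fact miscounted, or miscounted differently by arm. The documents contain no evidence of either.

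**What to change.** In section 7.4.1, flag concomitant AEDs by WHO-DD/ATC antiepileptic class, plus a short list of anti-seizure drugs coded in other classes. Apply the flag whatever the indication wording, and exclude records from the Rescue Medications page. Agree the list at blinded review before unblinding; section 6.9 already plans a data review to choose the most used AEDs. Use this one flag for the AED tables, the AED subgroups and the AED-change analysis in 8.2.3.

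The cost is a change of wording in 7.4.1 and one blinded review of the coded drug list. No new data are needed, because the coding is already planned. The downside is that an AED-class drug taken for a non-seizure reason will also count. That is acceptable here, since such a drug can still affect seizures.

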8. EFFICACY

The analysis of the Part 1 primary and secondary efficacy parameters will be performed on the mITT population for Cohort A and B independently, except where noted.

The Part 1 primary efficacy endpoint and key secondary efficacy analyses will be repeated on the PP Population for Cohort A and B independently, in order to assess the impact of major protocol deviations on the key inference.

All primary and key secondary variables will be analyzed for data obtained for the T+M period, and will be repeated for data obtained during the M period only.

8.1. MULTIPLICITY STRATEGY AND TESTING HIERARCHY

The Part 1, Cohort A efficacy analyses will employ a serial gatekeeper strategy to maintain the Type 1 error rate at α =0.05 across the family of analyses that support the primary and key secondary objectives. The strategy specifies a hierarchy of significance tests where each test acts as a gatekeeper to the tests below it.

The hierarchy starts with the primary analysis comparing ZX008 0.8 mg/kg/day to placebo on the change in number of seizures that results in drops from baseline. The next steps in the hierarchy entail the comparisons for the key secondary endpoints.

• Change from baseline in frequency of seizures that result in drops in T+M in the ZX008 0.2 mg/kg/day group compared to placebo.

- Proportion of subjects who achieve a ≥50% reduction from baseline in the frequency of seizures that result in drops in the ZX008 0.8 mg/kg/day and 0.2 mg/kg/day groups independently versus placebo.
- Proportion of subjects who achieve improvement (minimally, much, or very much improved) in the Clinical Global Impression - Improvement (CGI-I) as assessed by the Principal Investigator comparing the ZX008 0.8 mg/kg/day and 0.2 mg/kg/day groups independently versus placebo.

Below is a complete list of steps in the testing hierarchy in order:

- 1. Compare ZX008 0.8 mg/kg/day to placebo on the change in frequency in seizures that result in drops per 28 days between the Baseline and T+M periods.
- 2. Compare ZX008 0.8 mg/kg/day to placebo on the proportion of subjects who achieve a ≥ 50% reduction from baseline in the number of seizures that result in drops.
- 3. Compare ZX008 0.8 mg/kg/day to placebo on the CGI-I at Visit 12.
- 4. Compare ZX008 0.2 mg/kg/day to placebo on the change in frequency in seizures that result in drops per 28 days between the Baseline and T+M periods.
- 5. Compare ZX008 0.2 mg/kg/day to placebo on the proportion of subjects who achieve a \geq 50% reduction from baseline in the number of seizures that result in drops.
- 6. Compare ZX008 0.2 mg/kg/day to placebo on the CGI-I at Visit 12

8.2. PRIMARY EFFICACY ENDPOINT AND ANALYSIS

8.2.1. Primary Efficacy Endpoint Definition

The Part 1 primary efficacy endpoint is the percent change from baseline in the frequency in seizures that result in drops per 28 days in the T+M period. The following seizure types from the DSD will be included in the frequency count of seizures resulting in drops, if for an individual subject, the seizure as listed in the eCRF has been confirmed and approved by the Epilepsy Study Consortium (ESC) as a 'drop seizure':

- atonic seizures [AS]
- tonic seizures [TS]
- tonic/atonic seizures [TA]
- generalized tonic-clonic seizures [GTC]
- secondarily generalized tonic-clonic [SGTC]

For each subject, the frequency of drop seizures will be calculated from all available data collected during the Baseline and T+M Periods. Subjects in the ZX008 0.8 mg/kg/day treatment group will be compared to those in the placebo on the frequency of drop seizures (DSF) during T+M adjusted for the frequency during Baseline using a non-parametric ANCOVA model.

The baseline period is the 28 days immediately preceding the date of Study Day 1. The T+M period is planned for 14 weeks. However, actual durations will be computed for

each subject based on the individual subject's start and stop dates for each period, except that if the baseline period is longer than 28 days, the frequency for the baseline period will be calculated with data from the 28 days immediately preceding the Study Day 1.

The frequency of drop seizures will be counted from the daily diary records provided by the Subject or Parent/Caregiver.

Responses to the DSD question about the frequency of seizure episodes will be handled differently according to the following response options.

Response	Number of seizures
No seizures	0
A single seizure	1
An episode of many discrete seizures	Based on the response to the Question 12 for frequency of episodes
A cluster of seizures back to back	This will be determined empirically dependent on the duration of the cluster event and the number of events reported in a discrete seizure event for subjects in the study.

Seizure Clusters

Seizure clusters are entered in the DSD by estimating the duration of the cluster in hours: minutes; seconds. For seizure clusters the number of discrete seizures that occurred during a cluster is not entered in the DSD. In order to estimate the number of seizures during a cluster, the number of seizures will be imputed using the seizure count and duration of seizures recorded for "an episode of many discrete seizures".

Specifically, episodes of discrete seizures include both an estimate of the number of seizures, and an estimate of the duration, categorized into 1 of 3 buckets: <2 minutes; 2-10 minutes; >10 minutes.

Study-level summary statistics using seizure events reported in the T+M period will be calculated for each bucket to determine the median number of seizures occurring in each bucket.

The median number of seizures will then be used to impute counts for seizure clusters:

- 'short' clusters (i.e., ≤59 minutes) will be the median number of seizures reported in discrete seizure events <2 minutes
- 'medium' clusters (i.e., 1-5 hours) will be the median number of seizures reported in discrete seizure events 2-10 minutes

• 'long' clusters (i.e., >5 hours) will be the median number of seizures reported in discrete seizure events >10 minutes.

For any individual subject, the frequency of drop seizures per 28 days during the baseline period (DSF_B) will be derived as follows:

$$DSF_B = \frac{28 \times Total\ number\ of\ drop\ seizures\ during\ the\ Baseline\ Period}{Total\ number\ of\ days\ in\ the\ Baseline\ Period\ with\ nonmissing\ diary\ data}$$

For each treatment group, the median and mean DSF_B will be calculated.

Similarly, for each subject, the frequency of DSF per 28 days for the T+M period (DSF $_{T+M}$ is derived as below:

$$DSF_{T+M} = \frac{28 \times Total \text{ number of drop seizures during the } T + M \text{ Period}}{Total \text{ number of days in the } T + M \text{ Period with nonmissing diary data}}$$

The percentage change from baseline for any individual subject will be estimated by $PCDSF_{T+M} = (DSF_{T+M} - DSF_B)*100/DSF_B$

The difference from baseline (CDSF_{T+M}) will be estimated by CDSF_{T+M} = DSF_{T+M} – DSF_B.

For each treatment group, descriptive statistics for DSF during baseline, T+M and M only, as well as the differences and % changes from baseline, will include the number of observations, mean, standard deviation, median, minimum and maximum, overall.

8.2.2. Part 1 Primary Efficacy Endpoint Analyses

T+M Period:

The primary analysis will compare the ZX008 0.8 mg/kg/day group to the placebo group for Cohort A using a two-sided test at the α =0.05 level of significance.

The primary endpoint will be analyzed using a non-parametric analysis of covariance (ANCOVA) model with treatment group (three levels; Placebo, 0.2 mg/kg/day, 0.8 mg/kg/day) and weight strata group (< 37.5 kg, \geq 37.5 kg) as factors, rank of baseline DSF_B as a covariate and rank of percent CDSF_{T+M} as response. Treatment group mean differences from placebo will be estimated via least squares means from the analysis model along with 95% confidence intervals.

The null hypothesis

$$H_0$$
: $\mu_{Z0.8} - \mu_P = 0$,

will be tested against the alternative

$$H_A$$
: $\mu_{Z0.8} - \mu_P \neq 0$,

where $\mu_{Z0.8}$ and μ_P represent the ZX008 0.8 mg/kg and Placebo group location parameter, respectively.

Rejection of the null hypothesis in favor of the alternative, in the presence of a statistically significantly smaller seizure frequency for the treatment group compared to the placebo group, (two-sided p-value <.05) will be regarded as evidence of a treatment benefit in favor of the 0.8 mg/kg group. A similar comparison of the location parameter for Z008 0.2 mg/kg/day vs. placebo will be regarded as evidence of a treatment benefit of the 0.2 mg/kg group. This is the 3rd key secondary endpoint.

Sample SAS code for the non-parametric ANCOVA described above is as follows:

```
Proc rank data=temp ties=mean out=ranktemp;
Var bsrd csrd;
Rank r_bsrd r_csrd;
Run;
proc glm data=ranktemp;
    class wtgrp trtp;
    model r_csrd = r_bsrd wtgrp trtp / SS3;
    lsmeans trtp / pdiff stderr;
```

where trtp = randomized treatment group (with codes 1, 2, 3 indicating placebo, 0.2 mg/kg, and 0.8 mg/kg groups).

```
r_bsrd = rank of baseline DSF_B,
r_csrd = rank of percent CDSF_{T+M}
wtgrp = weight group.
```

Additional statements may be used to obtain estimates and associated 95% confidence intervals.

